1. PURPOSE OF STUDY

COVID-19 infection during pregnancy is associated with increased risk of pre-eclampsia, preterm birth and stillbirth.¹ Pregnant women with COVID-19 have a higher rate of ICU admission and intubation than those who are not pregnant.² COVID-19 vaccine is recommended before pregnancy and during pregnancy to decrease the risk of severe illness and death. Pregnant women should also receive a booster dose of COVID-19 vaccine after the original series. A 2022 study showed the effectiveness of maternal vaccination against hospitalization for COVID-19 among infants was 52% overall, 80% during the delta period, and 38% during the omicron period.³ Importantly, studies show that the vaccine is safe and not associated with any negative maternal or infant outcomes.⁴

Despite the benefits of COVID-19 vaccination, only 71% of pregnant women were vaccinated for COVID-19 as of June 2022 (most prior to pregnancy), with a much lower rate of 58% among non-Hispanic Black women.⁵ Additionally, only 56% of pregnant women overall have received a booster, but only 39% of Black pregnant women have received a COVID-19 booster vaccine. **An effective intervention is needed to improve COVID vaccination rates for pregnant women overall, and particularly for Black women.**

Using participating OB/GYN offices affiliated with 3 health systems in [REDACTED], the **VAX-MOM COVID-19 intervention phase will implement a quality improvement initiative aimed at increasing maternal COVID-19 vaccination rates at participating sites.**

2. BACKGROUND AND RATIONALE

Burden of COVID-19

Pregnant women are at risk of significant morbidity and mortality from COVID-19 infection, compared to the general population. Complications include increased need for ICU care, need for extracorporeal membrane oxygenation, prolonged ventilation, and death.²

Effectiveness of maternal COVID-19 vaccination

Maternal IgG raised by vaccination during pregnancy crosses the placenta to the infant, and remains detectable in more than half of infants at 6 months of age. Early estimates suggest that vaccinating pregnant women after 20 weeks is 80% effective, and before 20 weeks is 32% effective at preventing hospitalization of infants younger than 6 months with COVID-19.⁶

Barriers to Vaccination

There are many barriers to COVID-19 vaccination for pregnant women. Patient Barriers include vaccine hesitancy, lack of knowledge of the benefits and risks of COVID-19 vaccine or protection for the baby, concerns about vaccine safety generally and during pregnancy due to misinformation, and low perceived susceptibility to infection.^{7,8} Provider Barriers likely include missed opportunities for vaccination, lack of a vaccine recommendation or weak endorsements by health providers⁹⁻¹² and various suboptimal practice operations.¹³⁻¹⁵ Since most women vaccinated during pregnancy receive their immunizations from their OB/GYN,¹⁶ it is critical for OBs to discuss, recommend, and offer immunizations. System Barriers include lack of audit and feedback, and lack of a standing orders as well as challenges with vaccine purchase and storage.^{11,17}

The VAX-MOM COVID-19 study will ultimately address multiple components by focusing on provider and staff communication, workflow optimization and vaccine rate feedback to overcome these barriers.

 - *As-Needed Data Development & Analysis Meetings* (State-level investigators, study coordinator, EHR report builders, data specialists, consultants as needed): discussion of data collection methods, EHR data extraction methods, data analysis, data storage/management.
- Keeping all study personnel abreast of prearranged study changes and subsequent regulatory determinations (e.g., changes to study measures, workflow procedures, study personnel, etc.) via a predetermined communication chain:
 - Core Leadership Team discusses necessary study change → Study coordinator submits amendment via sIRB → IRB notifies Study PI and study coordinator of regulatory determination → Study PI and coordinator notify Core Leadership Team → As appropriate, study coordinator will further notify local IRBs and site-level personnel and/or data specialists
 - Communication with study site personnel will most often take place during prescheduled meeting times, but in more urgent cases, will take place as soon as needed.

- Communication will be both verbal (during or outside of weekly meetings depending upon level of urgency) and written as needed (via e-mail, e-mail attachments, or the secure shared Box folder).
- Keeping all study personnel abreast of *unforeseen study events and subsequent regulatory determinations* (e.g., protocol deviations, breaches in confidentiality, subject/site withdrawal, etc.) via a predetermined communication chain:
 - Study personnel reports study event to PI → PI notifies study coordinator → PI and study coordinator notify IRB, as well as other study personnel as appropriate → any action requested by IRB is communicated to Core Leadership Team → As appropriate, study coordinator will further notify site-level personnel and/or data specialists
 - As described above, communication will be both verbal and written.
 - Also see section #16 “Data & Safety Monitoring Plan”

4. STUDY DESIGN & PROCEDURES

Brief Overview of Phase 2:

Using a clustered RCT (randomizing practices), we will allocate half of the practices within each health system to the VAX-MOM COVID-19 intervention and the other half to standard of care (control). We will measure the impact of the intervention on vaccination rates (primary outcomes) as well as rates of vaccination by subgroup (secondary outcomes) (see Table 4). Finally, if VAX-MOM COVID-19 is successful, we will provide the control practices with core intervention materials (e.g., learning module, rate feedback template) at the conclusion of the study.

Design and Procedural Details of Phase 2: (also see Figure 1 for Timeline)

Step 1) Deliver VAX-MOM COVID-19 training to randomized practices:

Randomization Details:

Practices will be the unit of randomization. We will assign practices using a covariate constrained randomization strategy. Practices will be stratified by health system, as well as arm assignment in the primary VAX-MOM trial. Within strata, we will perform constrained randomization to allocate practices to intervention/control arms, and ensure each arm has similar baseline COVID vaccination rates, percent of patients covered by Medicaid, number of OB providers, and number of patients. Specifically, we will use these variables to construct and evaluate a balance criterion, which is the sum of the squared difference between standardized group means on these variables. We will generate all possible combinations of eligible practices in 2 arms (using a SAS macro), and define an acceptable set of randomizations that result in balanced variables (generally the lowest 10% on the balance criterion). From this set of randomizations, we will select one set at random, and then randomly assign each practice to intervention vs control group.

Intervention Details:

Once randomization has been completed, and “intervention group” practices have been identified, multiple quality improvement (QI) techniques will be aimed at practice providers, nurses, and staff.

- **Identification of a “vaccine champion” at each intervention site:** At each site, the affiliated medical director or health system liaison will select one “vaccine champion” for each practice. Each identified vaccine champion will be e-mailed an Information Sheet (see “*InfoSheet_VaccineChampion...*” document) by the study coordinator, outlining the basic study goals as well as their involvement in tasks throughout the training and intervention adoption phases of the study (see “Consent Process” section). The position of vaccine champion is voluntary, and if they do not wish to accept the role, they may decline and another individual will be identified as a replacement. The vaccine champion will play a lead role throughout the study intervention, including:
 - assisting with the dissemination of e-learning training modules and the scheduling of follow-up site-specific meetings
 - acting to ensure training content is being appropriately adopted into practice workflow procedures
 - fielding questions from site personnel regarding the logistics of study interventions
 - acting as an ongoing liaison between the site personnel and study staff
 - leading regular discussions regarding immunization rate feedback with site personnel (see step 2 for further detail)
 - planning for and completing monthly PDSA cycles (see step 2 for further detail)
 - monthly completion of the “Practice Time/Cost Survey” (see step 4 for further detail)
 - participating in monthly learning collaborative meetings with the study team
- **Delivery/discussion of an online training module:** Each site will receive training focused on four main areas of content: a) the importance of COVID-19 vaccination during pregnancy, b) vaccine communication, c) optimization of workflow and d) review and resources (see Table 3). This training will be delivered first via an online e-learning platform, and next via an in-person or virtual site meeting.

Table 3: Training Module Content

General Topic:	Training Lessons:
Importance of COVID-19 vaccination during pregnancy	1- How bad is COVID-19 disease during pregnancy? 2- Why does ACOG recommend vaccination? 3- What are ACOG's COVID-19 vaccination recommendations?
Streamlining vaccine communication	4- A range of patient concern levels 5- For everyone: An evidence-based recommendation 6- For hesitant patients: Motivational interviewing 7- For patients who refuse at this visit
Optimizing workflow to increase vaccination	8- Strategies for increasing immunization rates 9- Putting the strategies into action
Review and resources	10- Test your knowledge 11- Provider & Patient Resources

- E-learning module dissemination: Module lessons will first be disseminated to practice site personnel via an e-mail link taking them to the Articulate/Rise 360 platform. The study coordinator will obtain e-mail addresses for the site personnel from either the health system liaison or the associated vaccine champion, and will then e-mail a training content link to all appropriate site providers, nurses, and staff. Attached to this initial e-mail will be an Information Sheet describing the study goals and training phase details, as well as their involvement throughout the duration of the 6-month QI intervention (see “*IntroEmail_TrainingPhase...*” and “*InfoSheet_TrainingPhase...*” documents; also see “Consent Process” section for more detail). After reviewing the Information Sheet and discussing any questions/concerns with study staff, site personnel will be asked to access and complete the training lessons prior to their scheduled site meeting.

Embedded at the conclusion of the online training module, will be a link to a brief REDCap survey (see “*TrainingModuleCompletionSurvey...*” document) to obtain information regarding those who have fully

completed the training. A list of practice personnel who have successfully completed the online training will be stored in a password-protected Excel file by the study coordinator. The names will not be linked with any other study data. The list will be accessible only by study staff for the purposes of confirming those who should receive MOC/CME/CNE credit for their participation and to calculate overall completion rates for each site.

- Site meeting: Following the online training, all site personnel will meet with study staff either in-person or via a virtual Zoom meeting. The meetings (both virtual and in-person) will be audio and video recorded using a laptop or handheld recording device (in-person meetings) or via the Zoom recording option (virtual meetings) (see “Audio/Video Recording” and “Privacy and Confidentiality” sections for more detail). These archived video files will allow for the review of meeting content by site personnel who were unable to attend the meeting live, or by those who simply wish to review the meeting discussion for a second time.

During the site meeting, study staff will briefly review online training content, allow time for the sharing of comments/questions from site personnel, and lead a discussion regarding the application of training content ideas specifically to that practice site. During this meeting, study staff will also present site personnel with their current immunization rates. Each designated vaccine champion will track meeting attendance or participation will be tracked via the Zoom “participant list.” The study coordinator will store this roster in a password-protected Excel file. The names will not be linked with any other study data. This list will be accessed for the purposes of confirming those who should receive MOC credit for their participation in the project, and for calculating overall attendance rates for each site.

- MOC/CME/CNE credit: To encourage the completion of online trainings and attendance at site meetings, providers and nurses will be offered CME/CNE credit for completing the online learning module, and providers will be offered MOC/QI credit for attending office systems change meetings and reviewing practice rates.

Step 2) Implement intervention ideas and monitor progress at intervention practices:

To monitor the adoption of VAX-MOM COVID-19 training content (changes in communication techniques, workflow optimization, etc.) at each practice site, each vaccine champion will participate in the following activities:

1. *Lead a discussion regarding immunization rate feedback* with practice providers, nurses, and staff on a monthly basis. The site-specific vaccination information will be obtained from either: 1) the EHR report builders for each health system, or 2) manual chart review (i.e., accessing eRecord to look up patient charts and

entering information into a REDCap data entry template) completed by study staff or the site's vaccine champion. Obtained vaccination information will be uploaded to the secure [REDACTED] Box folder. The project's data analyst will plug this vaccination information into a template that will create visual graphs and tables, allowing practice personnel to better understand trends within their site. The study coordinator will then disseminate the visual vaccination rate feedback to each site for review and discussion (see "*RateFeedbackTemplate...*" document).

2. *Develop PDSA cycle goals on a monthly basis utilizing knowledge about current workflow efficiency and data from vaccine rate reports.* Vaccine champions will utilize the PDSA template (see "*PDSAandTimeCostSurvey...*" document) to guide progress with their respective teams. The template will help them decide upon specific intervention activities appropriate for their setting, track those involved with each activity, compare results from the activity to previous performance, and focus on changes that may need implementation during future cycles. PDSA cycle logs will be sent to vaccine champions for completion via a secure REDCap survey.

For participating [REDACTED] practice sites, the 6-month intervention (entailing PDSA cycles described above) will be extended by 3-5 months (depending upon the original start date of the specific location) until April of 2024, to optimize vaccine intervention efforts and data collection during the peak of the COVID season.

During the 6+-month intervention phase, a study team member may observe intervention sites in-person in order to collect qualitative data regarding workflow and communication techniques as described in the sites' submitted PDSA cycle logs. Specifically, the study team member will document the ways in which the targeted intervention techniques are implemented within the practice (see "*InPersonObservationNotes...*" document). Observation notes will then be compared with submitted PDSA cycle log information and analyzed for consistency.

Of Note: Although study staff will observe OB/GYN practice personnel during patient encounters, practice patients will NOT be the target of the observation, and no identifying patient information will be collected. Rather, the focus of observation will be the select practice personnel only. Any patient-level information recorded during the observation will be done so in a generic manner such that the patient could not be identified on the basis of the notes (e.g., "*...when patient indicated that they did not want the COVID-19 vaccine, the nurse stated, 'The doctor may talk to you more about that when she comes in.'*").

3. *Complete the "Practice Time/Cost Survey" on a monthly basis (see step 4 for further detail).* The vaccine champion will track site personnel attending each rate feedback and PDSA discussion as well as their role (e.g., Ob/Gyn, nurse, desk

staff, etc.) within the practice. They will then complete a monthly REDCap survey reporting aggregate information regarding total time spent on project-specific activity (see “*PDSAandTimeCostSurvey...*” document).

Additionally, to monitor study staff efforts during this phase (to parallel surveys completed by practice champions), study staff will participate in the completion of a weekly “*Study Staff Time Survey*” (see step 4 for further detail).

Again, for participating █ practice sites, the 6-month intervention (including the Practice Time/Cost Survey and Study Staff Time Survey described above) will be extended by 3-5 months depending upon the specific location, to optimize vaccine intervention efforts and data collection during the peak of the COVID season.

4. *Participate in learning collaborative meetings* on a monthly basis with the study team. The vaccine champions from all participating intervention sites, along with the study team, will meet together as a group to discuss current COVID-19 information, intervention strategies/tips and overall project progress.

Step 3) Compare intervention vs. control practices:

Using the “RE-AIM” framework (see Table 4) we will compare intervention practices to control practices using multiple data sources. We will focus on one primary outcome and multiple secondary outcomes.

Primary Outcome: Following the conclusion of phase 2 (6-month duration), we will assess the “Effectiveness” of the intervention by comparing intervention group COVID-19 vaccination rates against control group COVID-19 vaccination rates.

Secondary Outcomes: Following the conclusion of phase 2 (6-month duration), we will assess the remaining “RE-AIM” domains including “Reach,” “Adoption,” “Implementation,” and “Maintenance.”

Table 4: Summary of Outcome Measures and Tools

RE-AIM Category	Outcome Measure(s)	Data Source
Reach	
• Number of patients seen in the practice within study period.• Number of providers/nurses/staff completing the training modules.	EHR data & training attendance records

Effectiveness	
 Primary Outcome: Rate of COVID-19 vaccination (intervention vs control) Secondary Outcomes: 
 COVID-19 vaccination rates by subgroups including (i) insurance groups, (ii) race/ethnicity, (iii) number of pregnancy, (iv) vaccine in prior year Flu and Tdap vaccination rates by subgroups including (i) insurance groups, (ii) race/ethnicity, (iii) number of pregnancy, (iv) vaccine in prior year 	EHR data
Adoption	
 Number and proportion of personnel involved in the VAX-MOM office changes (receiving MOC credit, attending in-office meetings) 	Training attendance records
Implementation	
 Provider and office staff perceptions of feasibility, acceptability, barriers and facilitators to implementation, adherence to intervention, perceived time and cost, and impact on patient flow. Perceived strength of vaccine recommendations. Perceived adherence to staff checking whether vaccine is due. Costs of implementing interventions 	Post-Intervention Survey & Time/Cost Survey
Maintenance	
 Sustainability 	Post-Intervention Survey

Details for EHR data extraction:

- **EHR Measure Description:** We will work with health system EHR report builders and our experienced analysts to build EHR reports which evaluate vaccination coverage at participating sites (see Table 5).

Baseline data was previously gathered during STUDY00007624, STUDY00005115 and STUDY00004408. The remainder of this data (COVID intervention data), as well as any missing baseline data from the protocols listed above, will be gathered under the current protocol STUDY00007717.

Table 5. Data obtained from EHR for women with live births during intervention period

(NOTE: any data missing from the baseline period may also be gathered during Phase 2)

Primary Information	
 COVID-19 vaccination status (both dates and type) Flu vaccination status (dates) Tdap vaccination status (dates)
----------------------------	--

Additional Information: Patient Demographics	
 • DOB • MRN • Date of Delivery • GA at delivery • Race/ethnicity 	
 • Insurance • Language • Parity • High risk status • Other social determinants
Additional Information: Practice Demographics	
 • Site • Provider type (resident, midwife, MD) 	

- **EHR Measure Procedures:** EHR data report builders for each health system will extract the requested information (data in Table 5, also see “*EHRData...*” document) using live births occurring from July 2022 until the conclusion of the study, and place into an excel file which will then be uploaded to a secure [REDACTED] Box “initial report” folder for the study team.

The data will be extracted for intervention and control sites both **a)** on a monthly basis, for the purposes of providing monthly rate feedback reports to intervention sites, and **b)** if needed, at the conclusion of the study to obtain any missing data from sites not obtained in the previous months.

Initial automated report files will go through an auditing process in which a small percentage of patient charts will be reviewed manually (i.e., charts accessed in eRecord) by study staff and compared to automated report findings. Study staff completing this process will have received the proper Epic/EHR training and clearance. During the auditing process, files will be placed temporarily in secure “SMDNAS Research Storage” folders, to reduce the risk of altering original report files, or confusing audited files for originals.

Once the auditing process is complete, the finalized EHR reports will be uploaded back into a secure [REDACTED] Box “final report” folder for analysis and/or for creation of the monthly rate feedback form by the [REDACTED] data specialist. De-identified analyzed data and/or the rate feedback reports will then be placed in a “analyzed data/rate feedback reports” folder on [REDACTED] Box by the data specialist, accessible by the study team. For monthly rate feedback reports, the study coordinator will then disseminate the vaccination rate reports for each site to all corresponding vaccine champions via secure e-mail.

In the event automated reports cannot be generated in a timely manner (i.e., as needed for monthly feedback or final analyses), study staff or vaccine champions will extract this same information by conducting manual chart reviews. A list of delivery MRNs will be passed from the health system liaison into [REDACTED] Box, to identify appropriate patient charts that should be reviewed. Study staff will then manually access patient charts in eRecord for the appropriate health system and enter the information indicated in Table 5 into a REDCap “Manual Chart Review Tool” (i.e., a form into which study staff can easily enter the information needed). Once manual data entry into REDCap has been completed, the information will be exported as an excel file and saved to the secure [REDACTED] Box “final report” folder (as auditing will not be needed).

Details for Post-Intervention Survey:

- **Survey Measure Description:** The Post-Intervention Survey (see “*VAXMOMCOVID_PostInterventionSurvey...*” document) is a survey consisting of Likert scale, multi-option and open-ended questions. The survey takes approximately 10 minutes to complete. The survey assesses opinions regarding COVID-19 infection and vaccination, patient vaccine refusal, barriers to vaccination, vaccine workflow, RSV vaccine, practice culture, and basic demographic information.
- **Survey Measure Procedures:** At the conclusion of phase 2, all providers (MD, residents, NPs, PAs and CNMs) and 1-2 select nurses from both the intervention and control sites will be asked to complete the survey. A notification e-mail (see “*NotificationEmail...*” document) may first be sent out by the health system liaison and/or Chair of Obstetrics and Gynecology affiliated with the appropriate health system.

Surveys will be e-mailed to providers and select nurses by project staff using the secure web application REDCap (see “*IntroEmail_PostInterventionSurvey...*” document). E-mail addresses will have previously been obtained from the health system liaison or vaccine champion and uploaded to the REDCap platform. After initial survey distribution, if the subject does not click on the survey link embedded within the e-mail, the REDCap platform will automatically disseminate reminder e-mails to the subject (identical content as initial invite e-mail). Once clicked, the survey link will first take potential respondents to the Survey Information Sheet for review (see “Consent Process” section for more details), and if they agree, will then allow them to continue to the full survey. Surveys will be sent in 3 “waves” in order to allow subjects from each health system to view their own system-specific Information Sheet (e.g., [REDACTED] subjects will first see the [REDACTED] Info Sheet, followed by the full survey). Subjects may answer survey questions at their own pace and may stop and restart at any time. At the conclusion of the survey, they will receive an automated confirmation message to assure them that the process is complete.

Step 4) Evaluate cost of the VAX-MOM COVID-19 intervention:

[figure not shown]
Practice Time & Cost Survey (see “*PDSAandTimeCostSurvey...*” document): A survey aimed at evaluating the amount of time and money devoted to VAX-MOM COVID-19 intervention activities will be sent by the study coordinators via REDCap to the vaccine champion for each site on a monthly basis. The survey will be completed by the vaccine champion using their best time/cost estimates pertaining to the month prior.

Study Staff Time Survey (see “*StudyStaffTimeSurvey...*” document): A survey aimed at evaluating the efforts of VAX-MOM COVID-19 study staff will be sent to study personnel on a weekly basis via REDCap.

Final Time & Cost Analysis:

Upon completion of phase 2 we will conduct a final time/cost analysis. Our two-fold cost measures are (a) total intervention cost to implement the VAX-MOM COVID-19 program aggregated at the three health-system level under a cost analysis and (b) cost per additional vaccination under a subsequent cost-effectiveness analysis.

[figure not shown]
Figure 1: Timeline of Intervention Phase Procedures

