17. DATA ANALYSIS PLAN

The primary outcome (receipt of 1+ COVID vaccine) is binary and our main explanatory variable will be an indicator for study arm. We will employ intent-to-treat analyses using generalized linear mixed models (GLMMs) with practice random effects, an approach recommended for group-randomized RCTs in which the goal is to estimate the causal effects of interventions on individuals, adjusted for clustering within groups. This method performs well in situations where the number of observations per cluster is large and for unequal cluster sizes. Models will assume a binomial distribution and a log link function in order to compare vaccination rates between study arms in terms of risk ratios. We will adjust for all practice-level variables included in the randomization balancing criterion, as well as patient-level race/ethnicity. Hypothesis tests will be two-sided with alpha = 0.05. Analyses will be performed

using SAS v. 9.4 (SAS Institute Inc., Cary, NC).

Power Analysis: We conservatively assume a control group vaccination rate of 50% (maximum variance). Adjusting for clustering of patients in practices, and assuming an intraclass correlation (ICC) of 1% (consistent with previous work), this sample size provides 80% power to detect an overall increase of 8.0 percentage point increase in vaccination rates between the QI intervention and control arms. This assumes a chi-squared test (a simplification of the planned mixed model analysis described above), an alpha of 0.05, and a sample size of 5,000 pregnant women organized into 16 practices per study arm.

Final Time/Cost Analysis:

Our two-fold cost measures are (a) total intervention cost to implement the VAX-MOM COVID program aggregated at the three health-system level under a cost analysis and (b) cost per additional COVID vaccination under a subsequent cost-effectiveness analysis. To derive a policy implication regarding the sustainability of programs, we will estimate costs and ICER estimates from the health system perspective.

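### The primary outcome is charted vaccination with no dose window and no independent source; only intervention practices get feedback on the charted rate, so better recording of earlier or outside doses could count as effect

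*Combined protocol and SAP*

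**What the plan says.** Section 17 of the combined protocol and SAP defines the endpoint: "The primary outcome (receipt of 1+ COVID vaccine) is binary". It gives no period in which the dose must fall and no place of administration. Table 4 in Section 4 names EHR data as the only source for the vaccination rates. Table 5 lists, for each woman with a live birth, the dates and type of COVID-19 vaccination, delivery date and gestational age at delivery. It has no field for where a dose was given or when it was entered.

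Under EHR Measure Procedures in Section 4, "The data will be extracted for intervention and control sites", so extraction is common to both arms. Accuracy is checked by an audit, described as follows: "a small percentage of patient charts will be reviewed manually (i.e., charts accessed in eRecord) by study staff and compared to automated report findings". If automated reports are late, for monthly feedback or for the final analyses, study staff or vaccine champions may abstract charts by hand, and that route is exempt from audit. Section 4, Step 1 places champions at intervention sites.

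The monthly rate reports go to intervention sites. There the champion's tasks under Step 2 include to "Lead a discussion regarding immunization rate feedback" with practice personnel each month, and to set PDSA goals from the same reports.

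**The concern.** A practice shown a low charted rate can raise it by giving doses or by entering doses the woman already had. With a one-or-more-dose outcome and no window, both turn a no into a yes. Section 1 says most vaccinated pregnant women were vaccinated before pregnancy, so earlier doses that could be entered late should be common. Section 2 lists "challenges with vaccine purchase and storage" among system barriers, which suggests that some doses are given outside the practice.

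The prompt to act on the charted rate differs by arm, so recording may improve more in the intervention arm. The audit would not show this: a dose missing from the chart is missing from both things compared. Nor would the analysis remove it. The model in Section 17 adjusts for the baseline vaccination rate, but a recording change that arises after randomization and differs by arm is left in the estimate.

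At stake are the meaning of a significant risk ratio and the cost-effectiveness result, because the ICER in Section 17 divides by the difference in vaccination rates. If, for illustration, 2 of an observed 8 points were recording, the true denominator would be 6 points and cost per additional vaccination would be understated by a quarter (6/8 = 0.75).

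**Working it through.** **Step 1. The plan's own power figure, to set the scale.** Section 17 gives a 50% control rate, 8.0-point increase, ICC 0.01, two-sided alpha 0.05, 5,000 women, 16 practices per arm and 80% power. The design effect is 1 + (m − 1) × ICC, where m is women per practice.

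- 5,000 in total, 32 practices: m = 156.25; design effect 2.5525; effective n per arm 2,500/2.5525 = 979; power 94.5%.
- 5,000 per arm, 32 practices: m = 312.5; design effect 4.115; effective n 5,000/4.115 = 1,215; power 97.7%.
- 5,000 in total, 16 practices in total: m = 312.5; design effect 4.115; effective n 2,500/4.115 = 608; power 80.0%.

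The stated 80% is reproduced only by the third reading, which is not what the text says. That is a separate matter. Here it means only that the first and third readings are both carried below.

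**Step 2. Spurious difference when the intervention has no true effect.**

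Spurious difference = V × e × (s_int − s_ctl)

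- V is true coverage: 50% (the plan's control rate) or 71% (the Section 1 figure for pregnant women).
- e is the share of vaccinated women whose only doses were given earlier or elsewhere. It is not in the documents; assumed 30% to 80%.
- s is the probability that such a dose is in the chart. The gain s_int − s_ctl is not in the documents; assumed 5 to 20 points.

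**Step 3. Chance of a significant result from recording alone.** This is the two-sided z-test at 0.05 with the effective n of Step 1 and the recorded control rate held at 50%, where variance is largest.

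| V | e | Gain (points) | Spurious difference (points) | Significant, 32 practices | Significant, 16 practices |
|---|---|---|---|---|---|
| 50% | 30% | 5 | 0.75 | 6.3% | 5.8% |
| 50% | 50% | 10 | 2.5 | 19.8% | 14.0% |
| 50% | 80% | 20 | 8.0 | 94.5% | 80.0% |
| 71% | 30% | 5 | 1.1 | 7.6% | 6.6% |
| 71% | 50% | 10 | 3.6 | 34.9% | 23.6% |
| 71% | 80% | 20 | 11.4 | 99.9% | 97.9% |

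The nominal rate is 5%.

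**Step 4. A second view of scale.** If true coverage were 71% and control charts showed 50%, 21 points would be unrecorded. Entering 0.08/0.21 = 38% of that gap in the intervention arm alone would give the full 8-point design effect; 0.04/0.21 = 19% would give 4 points. The 50% is the plan's maximum-variance assumption, not an observed charted rate, so this is an illustration.

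**Step 5. What existing dates can and cannot separate.** Delivery date and gestational age give the start of pregnancy, and dose dates place each dose before or after it and before or after the start of the intervention. Late entry of an old dose is therefore identifiable from Table 5 as it stands. An outside dose given during pregnancy and after the start is not: its date looks the same whether or not the intervention prompted it, and Table 5 does not show its source.

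**The case against.** Several points on the other side are sound.

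- A reader might infer that the intervention trains staff to check or update the vaccine record. Table 3 does not say so; its workflow lessons have only general titles. The nearest line, "Perceived adherence to staff checking whether vaccine is due", is an implementation outcome from the Post-Intervention Survey, which goes to both arms. What differs by arm is feedback and workflow change based on the charted rate.
- A reader might infer that inflation would occur in the intervention arm only. Control practices can enter outside doses too, and only the difference matters. Randomization is stratified by health system and by arm in the earlier trial, so both arms share report builders. This does not exclude divergence after randomization.
- A reader might infer that no planned field could separate charting from vaccination. For doses before pregnancy or before the intervention, the dates in Table 5 can.
- Section 2 says most women vaccinated during pregnancy are vaccinated by their OB/GYN. That limits outside doses during pregnancy, but not the pre-pregnancy doses of Section 1, and the supporting reference is a 2011-12 influenza coverage report.
- An outside dose taken after a stronger recommendation is a genuine effect and should count.
- The EHR data attachment cited beside Table 5 is not among the documents, so a source field or registry feed cannot be ruled out.

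These remove the absolute wording. They do not supply a dose window, an independent source or an audit that could see an unrecorded dose.

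**Conclusion.** The point holds as a gap in ascertainment, not as a demonstrated bias. The endpoint is the chart record, the audit checks the report against that chart, the fallback review is unaudited and may involve champions, and feedback on the charted rate goes to one arm. A larger recording gain in that arm would be read as effect.

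The documents do not show whether this happens or how large it is. The ranges of 0.75 to 8.0 points (50% coverage) and 1.1 to 11.4 points (71%) rest on assumed values for the share of earlier or outside doses and for the recording gain. At the low end the false-positive rate barely moves from 5%; only the upper assumptions make a spurious significant result likely. A registry feed equal in both arms would pull the figures down. Because the direction would favour the intervention and part of the check needs no new data, the plan should address it before analysis.

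**What to change.** Keep any recorded dose as the primary outcome and add two things.

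1. **A dose-date sensitivity analysis from existing fields.** Repeat the primary model counting only doses given during the pregnancy and on or after one intervention start date per randomization stratum, applied identically to intervention and control practices. Control practices have no start date of their own, and Section 4 indicates that start dates vary by location. Fixing the stratum date at the earliest start among its intervention practices would serve: a dose before that date cannot be an intervention effect.
2. **A dose-source field in both arms.** Add to the Table 5 extract whether each dose was given in the health system or entered as an outside or historical dose, with entry date where available. Report the arm effect separately by source. An effect confined to outside entries would call for caution but would not prove an artefact, since prompted outside vaccination is real.

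Cost: the first item needs no new data. Its event rate, and so its precision, will be lower, and it also counts boosters in women vaccinated earlier, so it answers a slightly different question. The second needs extra report columns and a minor IRB amendment, because the HIPAA waiver request in Section 7 rests on a minimal set of patient fields. Source or entry date may be incomplete at some sites and should then be reported as unknown, by arm.
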